10.7.4.4 Safety evaluation

AE is medically coded by MedDRA and counted according to the classification of SOC and PT. In addition, the collective adverse events will be counted according to the classification of systemic reaction and local reaction as specified by the protocol. The treatment emergency adverse events (TEAE) after inoculation are mainly counted and analyzed in this trial, that is, the AE occurred after first dose inoculation or the AE with aggravated severity after first dose inoculation. The AE incurred before first dose inoculation is listed. Unless otherwise stated, the following AE is TEAE.

The occurrence number, number of cases and incidence rate of all AE in each group, AE related to the vaccine study, AE unrelated to the vaccine study, AE of Grade 3 or above, AE of Grade 3 or above related to the vaccine study are calculated. The dose distribution, time distribution and severity of AE are statistically described. The list of AE related to the vaccine study, list of AE unrelated to the vaccine study and list of AE of Grade 3 and above are set out.

The occurrence number, number of cases and incidence rate of all AE in each group, AE related to the vaccine study and AE unrelated to the vaccine study are calculated, and the differences between groups are statistically compared by Fisher's exact test. The SAE list is set out.

10.7.5 Interim analysis

At present there's no plan to conduct a mid-term safety analysis. If such an analysis does take place later, independent statisticians from DSMB will issue an unblinded safety report accordingly. The safety evaluation will be carried out by DSMB. The interim analysis in this study is for safety analysis only and does not affect class I errors in the trial.

10.7.6 Processing of missing data

The missing data after inoculation of the immunogenicity endpoint neutralization antibody results are imputed by LOCF in this trial and the indexes such as antibody positive rate and positive seroconversion rate are further calculated derivatively. Processing of missing data in the safety endpoint is not considered. See the statistical analysis plan for the details of processing of missing data.

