8.7 Clinical endpoints

8.7.1 Primary endpoints

- “the positive seroconversion rate and antibody level of neutralizing antibody against COVID-19 virus 28 days after the whole immunization”
- The positive seroconversion rate of IgG antibody (ELISA method) against COVID-19 virus 28 days after the whole immunization

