8.8 Study plan

8.8.1 Phase II clinical study plan

For each age group, the phase II trial is only permitted, when safety and tolerability have been preliminary confirmed in the phase I trial 7 days after the 1st dose of the high-dose group.

Volunteers will be screened from the resident healthy adults aged 18 years and above in accordance with the principles of voluntary registration, informed consent, and compliance with inclusion and exclusion criteria. When enrolled, every subject will be given a code number and get the correspondingly numbered vaccine shot. Subjects in the 18-59-year-old group will receive the experimental vaccine or placebo according to the 2-dose 0-14 d or 0-28 d immunization schedule, or 3-dose 0-28-56 d immunization schedule, respectively. Subjects in the ≥ 60 -year-old group will receive the experimental vaccine or placebo according to the 3-dose 0-28-56 d immunization schedule. After each dose, the subjects need to stay on site for 30 min to see if there's any immediate response. During the following 7-day systematic follow-up observation, the subjects should record their daily observation results on the Diary Card. After each dose, subjects will receive a telephone visit on day 3 and an intensive visit on day 7 by the researchers, to verify the safety of the vaccination. Subjects should carry out safety observations on their own from days 8-28 after each vaccination. After each dose, subjects will receive a telephone visit on day 14, and an intensive visit on day 28 by the investigator, to verify the safety of the vaccination.

About 5 ml of venous blood will be collected from subjects in the 2-dose immunization group before the 1st dose and 14 and 28 d after whole immunization, and from subjects in the 3-dose immunization group before the 1st and 3rd dose and 28 d after whole immunization, respectively, in order to determine the serum antibody levels. See Tables 2-7 for visit time, time window and visit content for different age groups.

Table 2. Visit content and schedule for 0-28-56 d immunization group

Visit No.	V0	V1	V2	V3	V4	V5	V6	V7	V8	V9	V10	V11	V12	V13
Content	Pre-immune 0-7 d	Day 0	3-5 d after V1	7-8 d after V1	14-21 d after V1	28-35 d after V1	3-5 d after V5	7-8 d after V5	14-21 d after V1 天	28-35 d after V5	3-5 d after V9	7-8 d after V9	14-21 d after V9	28-35 d after V9
1	Informed consent	X												
2	Collection of demographic information	X												
3	IgG, IgM screening	X												

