10.5.4 Evaluation indexes and criteria

The positive seroconversion rate of SARS-CoV-2 antibody, GMT (or GMC), and GMI are taken as the evaluation indexes of immunogenicity.

Determination criteria of positive seroconversion of neutralizing antibodies: negative if antibody titer < 1:4; positive if antibody titer \geq 1:4. The antibody positive seroconversion is considered if antibody titer is < 1 : 4 before immunization and \geq 1 : 4 after immunization, or antibody titer is \geq 1:4 before immunization and the antibodies increase by \geq 4 fold increase after immunization.

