10.7.3.2 Immunogenicity evaluation data set

Full analysis set (FAS): all subjects who follow the principle of intention analysis (ITT), have been randomized, have completed at least one dose of vaccination, completed the pre-immunity evaluation of blood sampling, and have valid antibody values are included. The subjects with incorrect vaccine number should be evaluated for immunogenicity according to their primary randomized group.

Per protocol set (PPS): all subjects who have not violated the inclusion/exclusion criteria, have been randomized, have completed the full-course vaccination, completed all the blood collection before and post vaccination for immunogenicity evaluation, and valid antibody values are included. Among them, subjects meeting the following conditions are not allowed to enter PPS:

- 1) Those with severe information and data missing after randomization;
- 2) Those who have seriously violated the protocol;
- 3) Those who have received the wrong inoculation or incorrect dose;
- 4) Those who have received concomitant medications or concomitant vaccines that affect the immunogenicity evaluation.

The corresponding PPS should be defined for each time point of immunogenicity evaluation in the basic immunization stage. FAS and PPS are mainly used to evaluate the immunogenicity of vaccines.

Immune persistence set (IPS): all subjects who have undergone the immune persistence evaluation stage and completed blood sampling at the time point for immune persistence evaluation and have antibody values are included. The immune persistence set should be defined for 3 months, 6 months, and 12 months after vaccination.

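### LOCF for missing neutralizing antibody puts a pre-dose-3 titre (3-dose cohorts) or a day-14 titre (2-dose cohorts) into the day-28 primary endpoint of the FAS, probably understating it unequally

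*Protocol*

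**What the plan says.** Section 10.7.6 of the Protocol specifies last observation carried forward for neutralizing antibody after vaccination: "The missing data after inoculation of the immunogenicity endpoint neutralization antibody results are imputed by LOCF in this trial". It extends this to the derived binary endpoints: titres are "imputed by LOCF in this trial and the indexes such as antibody positive rate and positive seroconversion rate are further calculated derivatively". Only the details are left to the SAP, so a SAP consistent with the Protocol keeps LOCF.

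The affected endpoint is primary. Section 8.7.1 lists "the positive seroconversion rate and antibody level of neutralizing antibody against COVID-19 virus 28 days after the whole immunization".

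Section 8.8.1 fixes which samples exist before day 28. Blood is taken "from subjects in the 3-dose immunization group before the 1st and 3rd dose and 28 d after whole immunization, respectively". For the two shorter schedules it is taken from "subjects in the 2-dose immunization group before the 1st dose and 14 and 28 d after whole immunization".

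Section 10.5.4 defines seroconversion as a change from the pre-immunization titre: from below 1:4 to at least 1:4, or at least a 4-fold rise if the starting titre is already 1:4 or more.

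Section 10.7.3.2 defines the sets. The FAS needs randomization, at least one dose, a pre-immunization sample and valid antibody values; it does not say whether a post-dose value is required. The per-protocol set (PPS) needs every pre- and post-vaccination sample with valid values. Neither is named primary for immunogenicity. The immune persistence set is limited to subjects who "completed blood sampling at the time point for immune persistence evaluation and have antibody values are included".

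**The concern.** LOCF is unbiased only if the titre would have stayed where it was last seen. Here the further doses are given in order to raise it. In the 3-dose cohorts the most recent sample that can be carried is always one taken before the final dose, so the rule scores a subject on an incomplete course as if it were the day-28 result. In the 2-dose cohorts the same rule normally carries a post-course value. One rule thus does different things in different schedules.

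The error also differs by arm. A carried value understates a titre that is rising, as in vaccine recipients, and changes little where titres are flat, as in most placebo recipients. If missingness differs between the 5 µg and 10 µg arms, part of any dose difference is an artefact. Filled values enter the confidence intervals of section 10.7.4.3 as if observed, so the intervals do not reflect the uncertainty of the imputation.

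At stake are the estimates on which a trial of two doses and three schedules is read: GMT, seroconversion rate and the comparisons between them.

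**Working it through.** **1. What is carried into day 28**

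| Cohorts | Subjects | Latest sample before day 28 | If that is missing too |
|---|---|---|---|
| 3-dose (18-59 and ≥60) | 500 | before dose 3 | before dose 1 |
| 2-dose (0-14 d and 0-28 d) | 500 | 14 d after dose 2 | before dose 1 |

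A carried baseline titre is by definition unchanged, so under section 10.5.4 it is always a non-seroconversion.

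**2. The plan's own figure.** Section 10.7.2 states 99.99% power for 80% v 30%, 100 v 50 subjects, two-sided 0.05. This reproduces: 0.999995 (pooled normal), 0.999998 (unpooled), 0.99998 (exact Fisher).

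**3. Formulas.** Let m be the share imputed, p the true seroconversion rate, q the rate at the carried visit, and r the true day-28 titre divided by the carried titre.

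- Reported seroconversion = p(1 − m) + qm
- Reported GMT = true GMT × r^(−m)

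The Protocol gives no value for m and no human value for r or q; all three are assumptions. Its only titre course is the monkey study in section 5.1, with doses at 0, 7, 21 and 35 d. From 35 d to 49 d the GMT rose 1040/437 = 2.38 fold (5 µg), 905/394 = 2.30 fold (10 µg) and 1874/1194 = 1.57 fold (40 µg).

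**4. GMT multiplier**

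| r | m = 5% | m = 10% |
|---|---|---|
| 1.57 (lowest monkey value) | 0.98 | 0.96 |
| 2.3 | 0.96 | 0.92 |
| 4 (assumed) | 0.93 | 0.87 |
| 32 (baseline carried: true GMT 64, <1:4 scored as 2) | 0.84 | 0.71 |

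So r of 2.3-4 lowers the 3-dose GMT by about 4-13%. In the worst case a true GMT of 64 is reported as 53.8 (−16%) or 45.3 (−29%).

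**5. Seroconversion, vaccine arm at 80%**

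- Pre-dose-3 value carried, q assumed 40-60%: 78-79% at m = 5%, 76-78% at m = 10%.
- Baseline carried (q = 0), m = 10%: vaccine 80% → 72%, placebo 30% → 27%. That is 8.0 points lost against 3.0, and the difference falls from 50 to 45 points.

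**6. Power against placebo with baseline carried (exact Fisher).** 0.9999, 0.9996 and 0.9969 at m = 5%, 10% and 20%.

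**7. Contrasts**

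- Dose, both arms truly 80%, 5% v 15% missing, baseline carried: 0.80 × 0.95 − 0.80 × 0.85 = 0.08, a spurious 8 points. With a pre-dose-3 value carried and r = 4 the spurious GMT ratio is 4^(0.05 − 0.15) = 0.87.
- Schedule, equal true GMTs, r assumed 4 (3-dose) and 1.5 (2-dose): spurious 3-dose/2-dose ratio (1.5/4)^m = 0.95 at 5% and 0.91 at 10%.

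**The case against.** The case for leaving the plan alone has real force on several points.

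- **2-dose cohorts.** A reader might infer that LOCF always inserts a value from before the course was complete. For half the trial it normally inserts a day-14 post-dose-2 value, and the Protocol gives no titre course from day 14 to day 28 to show how far that is off.
- **Baseline carry-forward.** A reader might infer that missing vaccine recipients are scored near placebo level. That needs every later sample to be missing and the FAS to admit such subjects. The requirement for valid antibody values may exclude them. It is a worst case, not the expected one.
- **Placebo.** Placebo recipients are not scored exactly right either: section 10.7.2 assumes 30% placebo seroconversion, and a carried baseline removes part of that too.
- **PPS.** It requires all samples, so an analysis on observed values already sits beside the FAS.
- **Persistence visits.** Read alone, the LOCF sentence might seem to carry a peak into months 3 to 12. The immune persistence set admits only subjects with values at that visit, so there is nobody to fill.
- **IgG.** Section 10.7.6 is silent on IgG. Silence is not a conflicting rule, and the SAP may supply one.
- **Schedules.** Randomization is within each immunization group and the sample size rests on vaccine v placebo, so schedule contrasts are neither randomized nor powered.

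All of this narrows the point. It does not justify LOCF in the 3-dose cohorts, where the carried value necessarily precedes the final dose, and the PPS does not repair a FAS of equal standing.

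**Conclusion.** The point holds for the FAS. LOCF replaces a missing day-28 neutralizing titre with a pre-dose-3 value in the 3-dose cohorts and a day-14 post-dose-2 value in the 2-dose cohorts, with baseline possible only under the conditions above. GMT and seroconversion are probably understated, more in vaccine than placebo arms and more in 3-dose than 2-dose cohorts. Dose contrasts are at risk if missingness differs by arm.

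The likely size is modest: about 4-13% off the 3-dose GMT at 5-10% missing with a 2.3-4 fold rise, and 16-29% in the worst case. These rest on assumed missing rates, an assumed upper fold-rise and animal data for the lower one; the lowest monkey ratio would give only 2-4%. If few day-28 samples are missing, the effect is small.

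A reader might go further and conclude that the primary comparison with placebo is in danger. It is not: with equal missingness the bias is towards no difference, and power stays at or above 99.7% even with 20% of subjects carried from baseline. The harm is to estimates and contrasts, which is reason enough to replace the rule before unblinding.

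**What to change.** Delete LOCF from section 10.7.6 and replace it, before unblinding, with the following.

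- FAS analysis of neutralizing antibody on observed day-28 values, or a likelihood-based or multiple-imputation analysis of log titre by arm and visit within cohort.
- The same rule for neutralizing antibody and IgG, since both are in the primary endpoint.
- Missing counted as non-seroconverted only as a labelled sensitivity analysis. It gives the same seroconversion result as carrying baseline, so it belongs there as a conservative bound and not in the main analysis.

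The cost is one paragraph of Protocol and SAP wording. Observed values mean a slightly smaller analysed n; the model-based or imputation route means some routine programming.

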10.8 Initial analysis and additional analysis

Initial analysis: After the last subject completes the visit and immunogenicity test on Day 28 after the last immunization, all parties jointly complete the data review and database locking before unblinding for statistical analysis.

Updated analysis: Long-term safety observation and statistical analysis of immune persistence will be performed after completion of SAE observation at 12 months after full-course immunization and completion of antibody detection for immune persistence observation at 3, 6 and 12 months after full-course immunization.

10.9 Data safety monitoring board

A Data Safety Monitoring Board (DSMB) will be established in this study to supervise the study safety and enforcement in order to protect the ethical and safety interests of the subjects and the scientificity of the study. The DSMB is composed of clinical experts, vaccine epidemiologists and statistical experts independent of the sponsor, and none of them has any significant conflict of interest with the sponsor. The DSMB will assess the safety data of the trial (for the safety assessment time point in the interim analysis section) to ensure the risk/benefit ratio acceptable to the subjects in the treatment group. The DSMB will advise the sponsor on the measures it deems necessary to protect the subjects and on the overall safety assessment. The sponsor will make an analysis and make a decision on the continuation, revision or termination of the study according to the advice of the DSMB.

The meeting arrangements, composition, responsibilities and management of the DSMB will be described in a separate DSMB charter.

11. Monitoring of clinical trial

11.1 Responsibilities of all parties

The sponsor shall implement and maintain the quality assurance and quality control system and write the quality management documents to ensure that the trial is carried out in accordance with the regulations. The data, records and reports shall meet the requirements of the GCP and other regulations and protocols. Prior to the on-site registration of subjects, the investigator and the CRA will review the clinical protocol and all trial procedures, including information on the vaccine for the trial, procedures for obtaining informed consent, procedures for reporting adverse reactions/events, and procedures for completing the CRF and data management.

The principal investigator shall manage and clearly assign responsibilities to all participants in the clinical trial, and formulate the SOP for each group of the trial.

The personal information of the subjects shall be kept confidential. The CRF form or other documents provided to the sponsor shall be identified only by the subject code and random number. The identification lists and screening registration forms of the subjects (including complete name, age, and address) will be kept in the research files by the researchers. In accordance with GCP principles, the original data of each subject shall be allowed to be monitored, audited and reviewed.

The CRA shall conduct the on-site follow-up monitoring at a regular time interval, check the consistency of the original medical records with the information on CRF, their accuracy and completion in the monitoring and, in case of inconsistency or failure to complete CRF in time, urge the investigator to modify or complete as soon as possible. The CRA will evaluate the process of informed consent, the transportation and storage of vaccine for the trial, the documents for the trial and the progress of the trial. The inspector should check the researchers' compliance with the protocol (or protocol amendment), observe the trial procedure and discuss with the researchers when certain problems occur. make the monitoring logs to record the on-site monitoring and, after the trial, provide the sponsor with a copy of the monitoring record.

11.2 Personnel training

Prior to the start of the study, the sponsor and the principal investigator shall train the participants in the trial by meeting in terms of the summary protocol of the clinical trial, the trial implementation procedures, time arrangement, operation cautions and trial data filling. Any additional CRA or investigator in the trial process shall be trained separately. If the sponsor or the principal investigator deems it necessary, retraining can be conducted. Each training shall be recorded.

11.3 Calibration of instruments and equipment and standardization of thermometer and glassware

- The refrigerator is provided with a temperature record;
- The thermometer has been standardized;
- Syringes used for vaccine injection and blood collection are disposable sterile syringes. The manufacturer has the national production license, and the batch number and expiry date are recorded.

11.4 Vaccine management

A special person shall be assigned to manage the vaccine for the trial, establish the vaccine management system and record system and accept the supervision of the CRA in terms of vaccine handover, warehousing and storage, distribution and recovery records.

The sponsor shall provide an adequate quantity of vaccines, including backup vaccinebackup vaccines. The vaccine packaging must meet the requirements of the clinical trial, especially the requirements of the blind design of this study. The vaccine with damaged inner package or deteriorated vaccine shall not be used and shall be returned to the sponsor. If the cold chain system is damaged or the vaccine is frozen in the process of transportation and storage, the vaccine cannot be used. It shall be stored separately and marked with "X", managed by a special person and returned to the sponsor.

At the end of the trial, the investigator shall count all remaining vaccines. The total number of remaining vaccines and vaccines used shall be the same as the number of vaccine received by the investigator, and the remaining vaccine and their outer packages shall be returned to the sponsor.

11.5 Quality control of biological samples

The collected blood samples shall be subject to separation of serum under aseptic conditions, with the hemolysis rate $\leq 2\%$, contamination rate $\leq 1\%$ and error rate $\leq 1\%$.

After separation of serum, the serum shall be cryopreserved below -20°C and the temperature shall be below 0°C during transportation of the serum samples.

11.6 Quality control of documents

11.6.1 Original Materials

The original data shall include the demographic information, medical history inquiry results, physical examination results, laboratory examination results, vaccination record, blood collection records, concomitant drug, adverse events/reactions of the subjects and their processing and outcome. All information shall be recorded in the original logbook, which shall be properly kept by the investigator in a special room. The original data shall be archived in the research center, which is the basis for the subjects' participation in the clinical trial and the authenticity and integrity of the data.

The investigator shall fill in the original logbook carefully, accurately and timely, and all original data collected shall be recorded in the original logbook with a black sign pen on the same day. Mistakes shall be crossed out instead of be altered directly. The correct content shall be filed in next to it, signed and dated.

11.6.2 Sample case report form (CRF)

The electronic CRF is established by the “online electronic medical record entry system (EDC)” in this trial. Only the investigator and authorized staff will be allowed to access the EDC system during the trial. The electronic CRF is used to record the data of the clinical trial and is an important part of the clinical trial and study report. It shall be filled in with normative language according to the EDC system instructions and CRF filling instructions. Any electronic CRF data entry, verification, modification, cleaning and quality control process will be recorded in the EDC system. After data cleaning, the investigator shall confirm and electronically sign the data in each CRF.

All data on the electronic CRF are derived from and consistent with the original materials. All data recorded in the CRF shall be recorded in the original materials.

The CRA authorized by the sponsor shall have access to the CRF, informed consent form and all original data at any time.

Any amendments to the clinical trial exchanges, meetings, protocols and SOP by the sponsor, investigator and other relevant personnel shall be provided in writing. All documents agreed upon by both parties shall be made out in duplicate, saved and filed respectively.

